2. OBJECTIVES, ENDPOINTS, AND HYPOTHESIS

2.1. Objectives and Endpoints

2.1.1. Objectives

Primary objective

The primary objective of the study is to demonstrate that Super-Responders (SRe; defined as psoriasis subjects who receive on-label guselkumab treatment until week 20 and respond with a Psoriasis Area and Severity Index [PASI] score=0 at weeks 20 and 28) maintain control of disease until week 68 with prolonged treatment intervals of 16 weeks (100 mg q16w). *To be demonstrated in Study Part 2 (see Section 3.1 for study design).*

Secondary objectives

Secondary objectives are to evaluate

- whether subjects with short disease duration (≤ 2 years) show a more rapid and better guselkumab response compared to subjects with longer disease duration and whether subjects with shorter disease are more likely to maintain drug-free control of disease after guselkumab withdrawal. *To be evaluated in Study Parts 1, 2, and 3.*
- whether SRe with short disease duration and PASI=0 at week 116 (ie, remission for one year after withdrawal) will show sustained remission (ie, PASI=0) over two additional years compared to subjects with longer disease duration. *To be evaluated in Study Part 3.*
- whether SRe with short disease duration and PASI>0 to ≤ 5 at week 116 (ie, partial relapse for one year after withdrawal) will show continued loss of response or stabilization of disease worsening over two additional years compared to subjects with longer disease duration. *To be evaluated in Study Part 3.*
- whether different treatment intervals (weeks 28 to 60: guselkumab 100 mg q8w vs. guselkumab 100 mg q16w) affect the maintenance of drug-free control of disease after 68 weeks of guselkumab treatment. *To be evaluated in Study Part 3.*
- the safety and tolerability of guselkumab in subjects with moderate-to-severe plaque-type psoriasis.

Note: disease duration will be calculated from date at which first symptoms (plaque) were reported by subject to date of screening visit.

Exploratory objectives

The following objectives are to be explored in the mechanistic biomarker substudies:

- characterization of the immune cellular and molecular composition at baseline (week 0) and changes (quantitative and qualitative characterization) in the lesional skin of subjects during treatment with guselkumab as determined by fluorescence activated cell sorting (FACS)-based analysis. *To be explored in substudy 1*

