1.1. Objectives and Endpoints

1.1.1. Objectives

Primary objective

The primary objective of the study is to demonstrate that Super-Responders (SRe; defined as psoriasis subjects who receive on-label guselkumab treatment until week 20 and respond with a Psoriasis Area and Severity Index [PASI] score = 0 at weeks 20 and 28) maintain control of disease until week 68 with prolonged treatment intervals of 16 weeks (100 mg q16w). *To be demonstrated in Study Part 2.*

Secondary objectives

Secondary objectives are to evaluate

- whether subjects with short disease duration (≤ 2 years) show a more rapid and better guselkumab response compared to subjects with longer disease duration and whether subjects with shorter disease are more likely to maintain drug-free control of disease after guselkumab withdrawal. *To be evaluated in Study Parts 1, 2 and 3.*
- whether SRe with short disease duration and PASI=0 at week 116 (ie, remission for one year after withdrawal) will show sustained remission (ie, PASI=0) over two additional years compared to subjects with longer disease duration. *To be evaluated in Study Part 3.*
- whether SRe with short disease duration and PASI>0 to ≤ 5 at week 116 (ie, partial relapse for one year after withdrawal) will show continued loss of response or stabilization of disease worsening over two additional years compared to subjects with longer disease duration. *To be evaluated in Study Part 3.*
- whether different treatment intervals (weeks 28 to 60: guselkumab 100 mg q8w vs. guselkumab 100 mg q16w) affect the maintenance of drug-free control of disease after 68 weeks of guselkumab treatment. *To be evaluated in Study Part 3.*
- the safety and tolerability of guselkumab in subjects with moderate-to-severe plaque-type psoriasis.

Note: Disease duration will be calculated from date at which first symptoms (plaque) were reported by subject to date of screening visit:

- Disease duration (days) = Date of visit 1 – date of first symptoms +1.

Exploratory objectives

The exploratory objectives are to be explored in the mechanistic biomarker substudies. These objectives are out of scope of this SAP.

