4.2.5. Pharmacokinetics Analysis Set

The PK analysis and the definition of the PK analysis set is out of scope for this SAP.

5. STATISTICAL ANALYSES FOR STUDY PART 3

Description of planned statistical analyses in Study Part 3 will focus on the comparison of the two study groups 3a and 3b which are without administration of study agent in Study Part 3 (ie, group **3a**: randomized to guselkumab 100 mg q8w in Study Part 2 vs. group **3b**: randomized to guselkumab 100 mg q16w in Study Part 2). Inferential statistics (ie, exploratory p-values, confidence intervals, etc.) will be provided only for the week 116/164/220 data of endpoints in Study Part 3.

Note 1: Statistical analysis of Study Part 3 will also include analyses of study data recorded before week 68. Data of Study Parts 1 and 2 will be summarized by descriptive statistics only. No exploratory inferential statistics (ie, p-values, confidence intervals, etc.) will be provided for the data of Study Parts 1 and 2.

Note 2: Subjects of group 3a and 3b who start re-treatment with guselkumab within Study Part 3 (up to week 116) will be evaluated only up to the study visit R0 at which PASI >5 is shown. If PASI was ≥ 3 already at week 68 the subject will not be evaluated for Study Part 3 in the scope of this SAP; a separate SAP will describe the analysis of the re-treatment phase.

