5.4. Major Secondary Endpoint(s) Analysis

Statistical analyses will be descriptive and exploratory only. They will be performed for the Intent-to-treat analysis set and, if requested, the Per-protocol analysis set.

Major secondary endpoints of this study in Study Part 3 are:

- Proportion of subjects with short (≤ 2 years) and longer (>2 years) disease duration who achieve an absolute PASI score of 0, ≤ 1 and <3 at weeks 116, 164, and 220, per study group
- Proportion of subjects who retain disease control (ie, absolute PASI score <3 at all visits) from week 68 through week 116, from week 68 through week 164, and from week 68 through week 220, for subjects with short (≤ 2 years) and longer (>2 years) disease duration per study group.

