- An additional frequency table will be provided for the number and proportion of subjects starting re-treatment after week 68 to week 116, after week 116 to week 164, and after week 164 to week 220; proportions will also be broken down by disease duration subgroups.
- The proportion of subjects with PASI or DLQI response by visit will be evaluated twice, first using the NRI approach and second the OC modified approach (applied to all visits after week 68).
- In addition, all efficacy scores (PASI, DLQI, PSSD, BSA, and NAPPA) by visit and changes from baseline will be presented only for visits with PASI $<$ 5 (OC modified, applied to all visits after week 68), with subgroups A and B (see Section 5.8.8).
- The endpoints PASI values over time in subjects with PASI $>$ 0 and \leq 5 at week 116 and PASI values over time in subjects with PASI \geq 0 and \leq 5 at week 116 will not be evaluated for the Week 220 analysis.
- Proportions of subjects with DLQI response (0/1; $<$ 5) by visit will be given by subgroups A and B only.
- DLQI categories will not be evaluated for the Week 220 analysis.

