Subgroup analyses will be performed on both, the ITT and the PP analysis set (if evaluated), after the rule for handling of protocol-prohibited medication/therapy has been applied using non-responder imputation for binary endpoints (for the proportion of subjects with DLQI values falling in quality-of-life categories: observed cases analysis) and observed cases analyses for time-to-event endpoints. The decision whether the PP should be used for the subgroup analyses was taken at the Data Review Meeting for the Week 116 analysis of Study Part 3: No PP analysis will be performed.

For each subgroup category the subgroups will be compared by statistical testing for the total of subjects (not separately for group 3a and 3b); the only exception where this will not be done are the subgroups created based on the prior psoriasis therapy regimen. Figures to display subgroups will be generated for the time to end of the treatment-free period.

Update before the final analysis:

The subgroups C to H will not be evaluated for the Week 220 analysis of PASI response (PASI = 0, <= 1, < 3, Retain disease control).

In contrast, for the time-to-event endpoints Loss of disease control and End of the treatment-free period, the following subgroups will be evaluated in addition to previous defined subgroups A to H:

- I: Age at baseline
 - Younger subjects (age < median age)
 - Older subjects (age >= median age)
- J: BMI at baseline
 - Thinner subjects (BMI < median BMI)
 - Thicker subjects (BMI >= median BMI)
- K: Sex
 - Female subjects
 - Male subjects.

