6.2. Appendix 2 Changes to Protocol-Planned Analyses

No important changes from the planned analyses specified in the protocol and its amendments were applied.

However, the time point of analyses is changed slightly. While the CSP states that “interim analyses are planned after all subjects have completed their visit at week 116 (or at week 144 in case of subjects entering the re-treatment arm in week 116) and at week 164 (or at week 192 in case of subjects entering re-treatment arm in week 164). The final analysis will be performed after all subjects have completed their visit at week 220 (or at week 248 in case of subjects entering the re-treatment arm in week 220)”, it was decided to split the analyses of group 3a/3b subjects and the analyses of group 3c subjects (re-treatment phase). By this, the results for the week 116/164/220 analyses of study groups 3a and 3b will be available as soon as possible. A separate SAP will be written for the analysis of the re-treatment phase that will include – beneath the group 3c – also the analysis of study group 2d (subjects who entered the re-treatment phase already in study part 2).

In addition, some new analyses have been added to the evaluation; see section 5.6 for details.

The initial SAP, prepared before the Dry-run meeting for the first interim analysis (week 116), was updated several times during the course of the study:

- Changes introduced before the Week 116 analysis:
 - The windows for the week 28, 68, 116, 164 and week 220 visits are expanded.
 - For LOCF, the earliest visit used for carrying forward is the week 68 visit.
 - Statistical testing for binary endpoints is also performed for the OC analysis.
 - For binary endpoints, a modified OC analysis is done to exclude visits with PASI>5.
 - Subgroups are compared by statistical testing.
 - The analysis of adverse events excluded AEs starting on the day of the R0 visit.
- Change introduced before the Week 164 analysis:
 - Demographic data are displayed separately for each subgroup.
- Changes introduced before the Week 220 analysis:
 - The subgroups C to H are not evaluated for the analysis of PASI and DLQI response.
 - For the time-to-event endpoints, subgroups I to H are added.
 - All efficacy endpoints (PASI, DLQI, PSSD, BSA, and NAPPA scores and changes from baseline) by visit are presented only for visits with PASI < 5 (OC modified), with subgroups A and B.
 - PASI and DLQI response by visit are evaluated for NRI and OC modified.

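### At week 220 no analysis separates subjects by their week-116 PASI, so two secondary objectives have no dedicated analysis over the two added years, and the by-visit score tables omit visits at PASI 5 or above

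*SAP*

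**What the plan says.** Protocol 2.1.1 and Part 3 SAP 1.1.1 list two secondary objectives that condition on PASI at week 116 and compare short with longer disease duration. The first takes Super-Responders with PASI=0 at week 116 and asks whether those with short duration "will show sustained remission (ie, PASI=0) over two additional years compared to subjects with longer disease duration". The second takes those with PASI >0 to ≤5 and asks whether they "will show continued loss of response or stabilization of disease worsening over two additional years compared to subjects with longer disease duration".

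Part 3 SAP 5.6 specified two descriptive tables of PASI by visit, by study group and disease duration. One was for subjects with PASI >0 to ≤5 at week 116, the other for PASI ≥0 to ≤5. The update before the final analysis states that both "at week 116 will not be evaluated for the Week 220 analysis". Appendix 2 records the removal in general terms, and the version history gives fewer tables as part of the reason for version 4.0.

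The same update says that the efficacy scores "by visit and changes from baseline will be presented only for visits with PASI" below 5, under the label OC modified, for visits after week 68. Elsewhere that label has another meaning: Appendix 2 says that "a modified OC analysis is done to exclude visits with PASI>5", and 5.4.3 uses the same threshold. Section 5, Note 2, says that subjects who start re-treatment "will be evaluated only up to the study visit R0 at which PASI >5 is shown".

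**The concern.** Both objectives ask a conditional question: given the same skin state one year after withdrawal, does disease duration predict what happens over the next two years? Answering it requires splitting subjects by that state. Without the split, a better pooled result in short-duration subjects has two readings. They may hold remission or stabilise better from week 116 onward, or they may only have arrived at week 116 in better condition. The study report would then carry two secondary objectives with no dedicated result over their stated period.

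The score filter adds to this. A PASI-by-visit table that leaves out visits at 5 or above cannot show worsening to that level, which is part of what the second objective asks about.

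**Working it through.** **1. Do the retained week-220 analyses cover the objectives?**

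| Retained analysis | Starting point | Separates PASI=0 from >0 to ≤5 at week 116? |
|---|---|---|
| Proportions with PASI 0, ≤1, <3, ≤5 (Part 3 SAP 5.4.3, 5.6) | each visit on its own | No |
| Proportion who "retain disease control (ie, absolute PASI score <3 at all visits) from week 68 through week 116", and through weeks 164 and 220 (5.4) | week 68 | No; threshold <3, not 0 |
| Time to PASI >5 (5.5.1.1) | week 68 | No |
| Treatment-free time (5.6) | last Part 2 injection | No |
| Re-treatment starts by period (5.6 update) | after weeks 68, 116 and 164 | No; by disease duration only |
| Subgroup H (5.8.8) | PASI at week 68 | No |
| Re-treatment SAP (4.2.1, 5.1.1) | R0 and up to five earlier visits | No; re-treated subjects only, so no view of stabilisation |

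Even subgroup H goes for the response endpoints: "The subgroups C to H will not be evaluated for the Week 220 analysis of PASI response". It stays for the time-to-event endpoints. No table for PASI=0 alone at week 116 was ever specified.

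**2. Coverage of the added period.** Weeks 116 to 220: 220 − 116 = 104 weeks. The week-164 analysis reaches 164 − 116 = 48 weeks, and 48/104 = 46%.

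**3. Can the retained proportions be rearranged into the answer?** The overall safety SAP (section 4) gives 273 subjects starting withdrawal and 227 re-treated from it. At most 273 − 227 = 46 were never re-treated, so at most 46/273 = 16.8% can have PASI=0 at week 220. Let p be the share with PASI=0 at week 116 and q the share at week 220. The share of the week-116 clear group that is clear at week 220 is known only to lie between max(0, p + q − 1)/p and min(p, q)/p. The documents do not give p; assume 20% to 50%, with q at its ceiling:

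- p = 20%: 0 to 0.168/0.20 = 84%
- p = 50%: 0 to 0.168/0.50 = 34%

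The separate proportions do not determine the conditional one.

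**4. What pooling can do.** Assume relapse between weeks 116 and 220 of 20% from PASI=0 and 60% from PASI >0 to ≤5, identical in both duration groups. With s the share at PASI=0 at week 116, pooled relapse is 20s + 60(1 − s) = 60 − 40s.

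- Short duration, s = 0.6: 60 − 24 = 36%
- Longer duration, s = 0.3: 60 − 12 = 48%

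This is a 12-point difference with none inside either stratum. For share differences of 0, 10, 20 and 30 points the artefact is 0, 4, 8 and 12 points. It equals the between-stratum relapse gap times the share difference, so halving the gap from 40 to 20 points halves the 12 to 6.

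**5. The cut-off.** Protocol Attachment 2 weights integer products by 0.1, 0.3, 0.2 and 0.4, so PASI moves in steps of 0.1. Enumeration shows that all 21 values from 3.0 to 5.0 can occur. Keeping PASI <5 caps the tables at 4.9; excluding PASI >5 caps them at 5.0. The two rules differ at one value, 5.0, which the plan classes as fluctuating disease and which does not trigger re-treatment in Part 3. Under either rule the R0 visit of a relapsing subject is absent from the score tables, and 227/273 = 83% of subjects relapsed.

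**The case against.** The strongest counter-case has four parts.

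- **No protocol endpoint was dropped.** The endpoint list has none conditional on week-116 PASI, SAP 5.6 introduced the two tables as additions to the protocol, and all of Part 3 is exploratory. This stands, and it limits the severity. The gap is between stated objectives and analyses.
- **The loss is smaller than two tables to none suggests.** The table for PASI >0 to ≤5 remained in the plan for week 164, so the second objective had a description for 48 of the 104 weeks. The PASI ≥0 to ≤5 table mixed the two states and matched neither objective. For the first objective nothing was lost, because nothing suitable existed. All true, but none of it supplies a two-year analysis.
- **Relapse by disease duration is still reported** through non-responder imputation, time to PASI >5 and re-treatment starts by period. Starts after week 116 largely concern subjects not above PASI 5 at week 116. That helps with continued loss, but it still combines subjects who were clear with those in partial relapse.
- **The cut-off is probably a slip and affects one score.** Plausible, and a one-word correction settles it. Loss of the R0 visit comes from the modified-OC idea itself rather than from the choice of 5.0, and relapses still count in other analyses. The consequence is confined to the descriptive score tables.

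Two cautions about the remedy are fair. Time to first PASI >0 would be a new endpoint, defined after the sponsor was unblinded for the week-68 analysis and assessed only every 12 weeks. Cells for sustained PASI=0 will also be small, since at most 46 subjects were never re-treated and that number includes any who stopped early or ended at week 116 under the unamended protocol.

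**Conclusion.** The concern holds. At week 220 the number of tables selecting subjects by week-116 PASI within 0 to 5 falls from two to none, and no retained analysis separates PASI=0 from PASI >0 to ≤5 at that visit. The full two-year comparison in both objectives therefore has no dedicated analysis. For sustained remission the gap predates the update.

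The trace of objectives to analyses and the cut-off conflict rest on the text alone. The 12-point figure and the 0 to 84% and 0 to 34% bounds rest on assumed rates and shares. They show what pooled results can hide and do not estimate this trial's bias. Because Part 3 is exploratory, the primary non-inferiority result is unaffected. The change should be made, but it is not critical to the trial's main conclusion.

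**What to change.** For the week-220 analysis:

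1. Reinstate PASI over time for subjects with PASI >0 to ≤5 at week 116, by disease duration and including the R0 value. Add time from week 116 to PASI >5.
2. For subjects with PASI=0 at week 116, report by disease duration the proportion with PASI=0 at all visits through week 220, and a Kaplan-Meier estimate of time to first PASI >0. Label these as late exploratory additions.
3. In both, include only subjects who continued beyond week 116, whom Part 3 SAP 5.2 already counts. Otherwise those who finished at week 116 under the unamended protocol could be imputed as non-responders.
4. Show by-visit scores on all observed visits up to and including R0, with n per visit and a note that later visits describe only subjects still in withdrawal. Keep OC modified as a supplement, with one cut-off throughout.
5. Record the changes in Appendix 2.

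The cost is a few descriptive tables from data already collected; the main table in item 1 was already specified for earlier analyses. If item 4 is thought too much, reconciling the cut-off and including R0 in the table in item 1 is the minimum.

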5.7. Safety Analyses

All safety analyses in Study Part 3 will be based on the Safety analysis set. Data from the safety follow-up at week 72 (study groups 2c and 3c) will not be included in the Study Part 3 analyses; last visit to be included for the Study Part 3 analyses is week 116/164/220 or R0 visit in case re-treatment was started. Safety data, including but not limited to, adverse events (AEs), serious AEs, infections, serious infections, and changes in vital signs, will be summarized by study group and overall. AEs will be summarized by Medical Dictionary for Regulatory Activities (MedDRA) system organ class (SOC) and Preferred Terms (PT) for each study group and overall.

For all continuous safety variables, descriptive statistics will include the N, mean, standard deviation, median, quartiles, minimum, and maximum. Categorical variables will be summarized using frequency counts and percentages.

5.7.1. Extent of Exposure

The number and percentage of subjects who received study agent during Study Parts 1 and 2 will be summarized. Descriptive statistics will be presented for the number of study agent administrations.

5.7.2. Adverse Events

The verbatim terms used in the eCRF by investigators to describe adverse events will be coded using the Medical Dictionary for Regulatory Activities (MedDRA). Any AE occurring after the day of the week 68 visit until the day of the week 116/164/220 visit (or the R0 visit, if applicable) in Study Part 3 will be included in the analysis. If the onset date is recorded partially only or is completely missing, then the event will be considered for analysis unless it is known to be prior to the week 68 visit based on partial onset date or resolution date. In case a subject missed the week 68 visit, the date of the week 68 visit will be estimated as 8 weeks (56 days) after the week 60 visit.

For each adverse event, the number and percentage of subjects who experience at least one occurrence of the given event will be summarized by study group and overall. Summary tabulation will also provide the number of events, if applicable.

Summary tables will be provided for:

- AEs
- Serious AEs (SAEs)
- AEs by severity
- AEs by relationship to study agent
- Infections
- Serious infections
- Injection site reactions.

In addition to the summary tables, listings will be provided for subjects who:

- Had (S)AEs.

Deaths will be displayed by study group. Frequencies for the following parameters will be included in the summary table:

- Number of subjects who died
- Cause of death
- Relationship to study agent (yes/no) (yes includes the following eCRF items: possible, probable, very likely).

A listing of subjects who died will also be provided.

Any AE occurring after the day of the week 68 visit until the day of the week 116/164/220 visit (or the day before the R0 visit, if applicable, ie, the day of the R0 visit is excluded) in Study Part 3 will be included in the analysis.

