5.1. General Considerations

The following general analysis definitions refer only to the Re-treatment phase.

The statistical analysis of the Re-treatment phase will be exploratory. Inferential statistics (ie, confidence intervals) will be provided only for the visit R24 data of endpoints in the Re-treatment phase. With the exception of the secondary endpoint (PASI <3 at visit R24), all other summary tables will be purely descriptive (for comparison of subgroups see below).

Descriptive statistics will include counts and proportions for categorical data, and mean, SD, median, interquartile range, and range, for continuous data. Graphical data displays will also be used to summarize the data.

Time-to-event endpoints will be analyzed using the Kaplan-Meier product limit method to estimate the survival distributions and the median time-to-event.

For selected endpoints, subgroups will be analyzed to evaluate – among others – the effect of randomization to treatment frequency (performed for Study Part 2) and the effect of disease duration (assessed in Study Part 1 as stratification factor) on efficacy endpoints assessed after re-treatment was started; subgroups are defined in Section 5.8.8. Subgroups will exploratorily be compared using the two-sided unadjusted two-group Chi² test acc. to Wald (binary endpoints), the log-rank test (time-to-event endpoints) or a univariate analysis of covariance (ANCOVA) model with fixed effect for subgroup and baseline value as covariate (continuous endpoints).

Individual subject data listings will be presented parameter-wise and will be sorted by study site, subject's identification number and study visit, if applicable (without a preceding classification variable).

Note: Statistical analysis for safety of the Re-treatment phase will not include analyses of study data recorded before start of re-treatment, as safety for Study Parts 2 and 3 was already evaluated in previous analyses. However, the analysis for efficacy of the Re-treatment phase will include the preceding study visits before R0 (the start of the Re-treatment phase). For each subject, up to five pre-R0 visits will be selected based on the 12-week visit schedule, where visit R-1 is the regular visit before the R0 visit. Data of Study Parts 1, 2 and 3 will be included in the individual subject data listings.

A more detailed description of the planned statistical analyses is provided in the sections below.

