5.1.1. Visit Windows

As subjects do not always adhere to the protocol visit schedule, the following rules are applied to assign actual visits to analysis visits. Listed below are the visit windows for analysis and the target days for each visit. The reference day is Re-treatment Day 1 (for definition see section 5.1.3). If a subject has two or more actual visits in one visit window, the visit closest to the target day will be used as the protocol visit for that visit window. Additional or unscheduled visits will not be used in the summaries or analyses, but they can be used for determination of clinically important endpoints. If two actual visits are equidistant from the target day within a visit window, the later visit will be used.

Study visits of Study Parts 1, 2 and 3 taken place before re-treatment with guselkumab has been started will not be re-assigned to visit windows as they will not be included in tabulation; however, the (negative) relative day will be computed to be displayed in the individual data listings.

All assignments will be made in chronological order. Once a visit date is assigned to a visit window, it will no longer be used for a later time point except for the endpoint. Listed below in Table 2 are the visit windows and the target days for each visit of the Re-treatment phase.

Table 2 – Visit Windows for Analysis

Parameter	Analysis Period	Scheduled Visit	Time Interval (Label on output)	Time Interval (Day) *	Target Time Point (Day)
All	Re-trt	R0	Week R0	Not applicable #	1
		R8	Week R8	20 to 85	57
		R16	Week R16	86 to 127	113
		R24	Week R24	> 127	169
		R28	Week R28 (SFU)	Not applicable&	197

* Relative to Re-treatment Day 1. Time intervals for analysis are wider than the visit windows allowed per CSP.

In some subjects, the first re-treatment dose was given at an unscheduled visit after the R0 visit. For these, the R0 visit will have a negative relative day.

& No visit window is defined for the safety follow-up visit as no efficacy data are obtained at this visit.

If there are site visits outside of the defined windows above, final decisions on the allocation of the actual visit to an earlier or later planned visit or whether the data will not be included in the analysis will be made during the Data Review or Dry Run Meeting.

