5.7.2. Adverse Events

The verbatim terms used in the eCRF by investigators to describe adverse events will be coded using the Medical Dictionary for Regulatory Activities (MedDRA). Any AE occurring at or after the day of first re-treatment dose is considered to be treatment-emergent. If the onset date is recorded partially only or is completely missing, then the event is regarded as treatment-emergent unless it is known to be prior to the first dose of re-treatment based on partial onset date or

resolution date. All reported treatment-emergent adverse events (TEAEs) will be included in the detailed analysis.

For each adverse event (ie, Preferred Term) the number and percentage of subjects who experience at least one occurrence of the given event will be provided. Summary tabulation will also provide the number of events, if applicable.

Summary tables will be generated for:

- AEs
- TEAEs
- TEAEs by severity
- TEAEs by relationship to study agent
- TEAEs leading to discontinuation of study agent
- Infections
- Injection site reactions
- Serious TEAEs (TESAEs)
- Serious infections
- Serious injection site reactions.

In addition to the summary tables, listings will be provided for subjects who:

- Had (S)AEs
- Had AEs leading to discontinuation of study agent.

Deaths will be displayed by analysis group. Frequencies for the following parameters will be included in the summary table:

- Number of subjects who died
- Cause of death
- Relationship to study agent (yes/no) (yes includes the following eCRF items: possible, probable, very likely).

A listing of subjects who died will also be provided.

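### Adverse events from the R0 day to the day before a delayed first re-treatment dose fall in neither the Part 3 nor the Re-treatment adverse-event analysis (minor)

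*SAP*

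**What the plan says.** Three of the analysis plans matter here: those for Part 3 (drug withdrawal), for the Re-treatment phase and for the Overall safety analysis.

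- **Part 3 SAP, 5.7.2, closing sentence.** AEs count from after the week 68 visit to the week 116/164/220 visit, "or the day before the R0 visit, if applicable, ie, the day of the R0 visit is excluded". Appendix 2 (6.2) records this as a change made before the week 116 analysis: "The analysis of adverse events excluded AEs starting on the day of the R0 visit".
- **Part 3 SAP, 5.7.2, opening paragraph.** AEs count "until the day of the week 116/164/220 visit (or the R0 visit, if applicable) in Study Part 3 will be included in the analysis". Section 5.7 likewise names R0 as the last visit to be included when re-treatment was started.
- **Re-treatment SAP, 5.7.2.** "Any AE occurring at or after the day of first re-treatment dose is considered to be treatment-emergent", and "All reported treatment-emergent adverse events (TEAEs) will be included in the detailed analysis". Section 5.1.3 sets Re-treatment Day 1 at the first dose, not at the R0 visit.
- **Re-treatment SAP, 5.1.** The safety analysis "will not include analyses of study data recorded before start of re-treatment, as safety for Study Parts 2 and 3 was already evaluated".
- **Re-treatment SAP, 5.1.1, footnote to Table 2.** "In some subjects, the first re-treatment dose was given at an unscheduled visit after the R0 visit".
- **Overall safety SAP, 4.4 and 5.4.1.** The withdrawal window runs from the 91st day after the last verum dose to the day before re-treatment starts, or to study end if there is none. The re-treatment window opens at the first re-treatment dose.

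**The concern.** One plan closes its window by reference to a visit and the next opens its window by reference to a dose. The plans themselves say that the two dates can differ. For a subject dosed after R0, an AE that starts in between is too late for the Part 3 tables and too early for the re-treatment tables. The reason given in Re-treatment SAP 5.1 for leaving out earlier data, that it was already evaluated, is not true of those days.

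The interval is not an arbitrary one. Part 3 had no scheduled laboratory tests, physical examinations or tuberculosis evaluations (Part 3 SAP 5.7.3), whereas the protocol's re-treatment schedule has all of them at R0. An AE recognised through those assessments could well carry an onset date on or just after R0. What is at stake is the completeness of two sets of phase-specific tables (AEs, serious AEs, infections, serious infections). Separately, the two statements in Part 3 SAP 5.7.2 would lead two programmers to different counts.

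**Working it through.** The documents give no figure for this point, so the check is a comparison of date windows.

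**Inputs.** Set R0 as day 0 and the first re-treatment dose as day d (d ≥ 0). Let x be the day of AE onset.

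- Part 3, closing sentence of 5.7.2 and Appendix 2: counted if x ≤ −1.
- Part 3, opening paragraph of 5.7.2: counted if x ≤ 0.
- Re-treatment, 5.7.2: counted if x ≥ d.
- Boundary at the dose, as in the Overall safety SAP: withdrawal side counted if x ≤ d − 1.

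**Uncovered days.**

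- Closing sentence: days 0 to d − 1, which is d days.
- Opening paragraph: days 1 to d − 1, which is d − 1 days for d ≥ 1. For d = 0 nothing is uncovered, but day 0 is counted in both phases.
- Boundary at the dose: none, and no overlap.

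| Delay d (assumed) | Gap, R0 day excluded | Gap, R0 day included | Overlap, R0 day included | Gap, boundary at first dose |
|---|---|---|---|---|
| 0 | 0 | 0 | 1 | 0 |
| 1 | 1 | 0 | 0 | 0 |
| 3 | 3 | 2 | 0 | 0 |
| 7 | 7 | 6 | 0 | 0 |
| 14 | 14 | 13 | 0 | 0 |

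Under the rule that Appendix 2 says was applied, any delay of one day or more leaves a gap. Under either wording, a delay of two days or more does.

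**Possible size.** The Overall safety SAP (4.5) gives 227 subjects re-treated after entering withdrawal. The share delayed and the length of delay are not stated. Purely as an illustration, assume 5–10% delayed by 7–14 days:

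- Subjects: 0.05 × 227 ≈ 11 to 0.10 × 227 ≈ 23.
- Person-days in neither analysis: 11 × 7 = 77 to 23 × 14 = 322.
- For scale, 273 subjects entered withdrawal. If they averaged only 84 days of follow-up (an assumption; the first scheduled visit is 12 weeks after week 68), the total is 273 × 84 = 22,932 person-days. The gap would then be 77/22,932 ≈ 0.3% to 322/22,932 ≈ 1.4%.

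**Where the events do appear.** The Overall safety SAP's withdrawal set runs to the day before re-treatment starts, so it covers the interval. Where the interval lies within 90 days of the last verum dose, its Part 2 sets cover it (4.2, 4.3). Those sets do not replace the Part 3 tables. No 3a/3b split is specified for the withdrawal set, and day 91 (13 weeks) after a last verum dose at week 60 or 52 falls near week 73 or 65, whereas the Part 3 window opens after week 68.

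**The case against.** The strongest reply is that nothing goes missing from the trial. The Overall safety SAP was written to use AE data from the whole study, covers the interval, and tabulates and lists AEs, serious AEs, infections, serious infections and deaths. That stands. A reader might infer from the gap that these events vanish from the trial's safety reporting. They do not; they are absent only from the two phase analyses.

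A reader might also infer that R0 findings in these subjects are lost. They are not: the Re-treatment SAP summarises R0 laboratory values, vital signs, abnormal physical findings and tuberculosis evaluations (5.7.3). Only AE records with onset in the interval are affected. Nor do the documents support the inference that doses were held for safety. The Table 2 footnote gives no reason for any delay, so selective loss of safety-related events is possible but not shown.

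It can further be said that Re-treatment SAP 5.7.2 lists an AE table apart from the treatment-emergent one, and that 5.1 puts data from Parts 1 to 3 into the subject listings. Individual events may therefore be visible in listings. The scope of the separate AE table is unclear, but 5.1 keeps data from before re-treatment out of the safety analysis, so the table cannot be relied on to fill the gap.

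Finally, Appendix 2 shows which Part 3 rule was applied, and all these analyses are exploratory. Both points are fair. They bear on importance, not on whether the windows meet.

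**Conclusion.** The point holds as a minor error in the plan. For group 3a/3b subjects first dosed after R0, AEs with onset from the R0 day to the day before that dose are in neither the Part 3 nor the Re-treatment AE analysis, and the stated reason for leaving them out is wrong for those days. Where the dose was given at R0, the windows join without a gap under the rule in Appendix 2.

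The size is d days per affected subject. The number of subjects and the values of d are unknown, and the illustrative figures rest wholly on assumed delays. Because the Overall safety analysis picks the events up, the practical impact is probably small. That reassurance depends on reading its re-treatment start as the first dose, which its section 5.4.1 supports.

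The contradiction within Part 3 SAP 5.7.2, and between its closing sentence and 5.7, needs no assumption. One related case is open: the Re-treatment safety set requires at least one dose (4.3), so a subject who reached R0 and was never dosed would have no AE from R0 onward in either phase analysis. The documents do not say whether any such subject exists.

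**What to change.** In Part 3 SAP 5.7.2:

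- For subjects who start re-treatment, end the AE window on the day before the first re-treatment dose. State that this also applies when R0 falls at the week 116, 164 or 220 visit.
- For subjects who reach R0 but are never dosed, run the window to study end, as the Overall safety SAP does.
- Delete the opening wording that runs the window to the R0 visit, and bring 5.7 and Appendix 2 (6.2) into line.

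The cost is a few sentences in one plan and one date variable that is already collected. No new data are needed. The change closes the gap without overlap. It will not make the Part 3 counts equal those of the Overall safety analysis, because the two windows open at different times. If the tables are already final, add a footnote to the Part 3 and Re-treatment AE tables giving the number of subjects first dosed after R0 (and any never dosed), and the number of AEs and serious AEs with onset in the uncovered interval.
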